3.16 Analyses of the Exploratory Endpoints

The analyses of the exploratory endpoints will be performed on both ITT and PP populations unless stated otherwise.

- On the subset of patients that exacerbates and are treated with IV antibiotics (PEX subset population), the changes of select biomarkers in blood, serum and plasma (absolute neutrophil count, white blood cell count, lipidomics, inflammation markers, and oxidative stress markers), as well as FEV1, weight and BMI, from prior to the start of IV antibiotics to after the IV antibiotic treatment will be summarized by treatment group and analyzed using descriptive statistics. The mean changes will be compared between fenretinide and placebo using parametric and non-parametric statistics, where appropriate.
- The overall change in the PsA density in the sputum, from Baseline to Week 12 and Week 24, and the AUC of the CFU from Baseline to Week 24 will be the variables studied for this investigation. Data will be summarized by treatment group and analyzed using descriptive statistics. The mean changes and the AUC data will be compared between fenretinide and placebo using parametric statistics assuming the data meet standard pre-requisites for such analysis (normal or log-normal distribution and homogeneity of variance). Area under the curve from baseline to Week 24, will be calculated with a linear trapezoidal method.
- The overall change in lumbar spine bone mineral density, from Baseline to last follow-up on Week 28 will be summarized by treatment group and analyzed using descriptive statistics. The mean changes will be compared between fenretinide and placebo using parametric statistics assuming the data meet standard pre-requisites for such analysis (normal or log-normal distribution and homogeneity of variance).

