7.1.3 Secondary Endpoints

- The proportion of patients achieving normalization of AA, DHA and the AA/DHA ratio in plasma phospholipids, LAU-7b compared to placebo. In this study, the normalization means a value or ratio value reaching the mean observed in healthy controls ± 1 SD;
- The absolute and relative (%) change from pre-study in FEV₁ percent predicted on Days 21, 49, 77, 105 and 189 visits (3, 7, 11 and 15 weeks during treatment and approximately 4 weeks after treatment, respectively), as well as the relative (%) change in FEV₁ % predicted on Day 161 (24 weeks), LAU-7b compared to placebo;
- The effect on the time to first protocol-defined PEx, LAU-7b compared to placebo;
- The effect on the incidence of protocol-defined PEx, LAU-7b compared to placebo;
- The effect on the time to first antibiotic use (other than chronic inhaled antibiotics already started prior to trial or oral chronic azithromycin), LAU-7b compared to placebo;

- The effect on the number of antibiotic treatments (other than chronic inhaled antibiotics already started prior to trial or oral chronic azithromycin), LAU-7b compared to placebo;
- The effect on the number of days of antibiotic treatment (other than chronic inhaled antibiotics already started prior to trial or oral chronic azithromycin), LAU-7b compared to placebo;
- The change from pre-study in systemic markers of inflammation in whole blood (total white cell count and absolute neutrophil count), serum (hsCRP and serum amyloid A), and plasma (calprotectin, haptoglobin, IL-1ra, IL-6, IL-8 IL-10, G-CSF, ceruloplasmin and neutrophil elastase antiprotease complexes), LAU-7b compared to placebo;
- The changes from pre-study in body weight and BMI, LAU-7b compared to placebo;
- The overall change in the *PsA* density in the sputum, from baseline through 12 and 24 weeks of treatment, when measured by the difference in the Area Under the Curve (AUC) of the CFU, LAU-7b compared to placebo;
- The fenretinide steady-state pharmacokinetics, depicted by C_{min} plasma concentrations at the end of the first and sixth treatment cycle;
- To assess the impact on overall health, daily life, perceived well-being and symptoms measured with the CFQ-R (total and respiratory domain) from pre-study to 12 and 24 weeks, LAU-7b compared to placebo.

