12. Eligibility-defining laboratory tests including at a minimum, urinalysis (dipstick), hematology, serum chemistry, plasma retinol and retinol-binding protein, and pregnancy test if applicable;
13. A Night Vision Questionnaire will be self-administered;
14. Complete ophthalmological examination (includes examination of visual acuity, examination for amblyopia, examination of eyelids, conjunctiva, cornea, pupillary reactions to light and accommodation, low contrast visual function (Contrast Sensitivity), specific dark adaptation tests (see note in Section 11.5), lens, vitreous humor, fundus examination of retina and retinal vessels, fundus visualization of optic nerve and macula), will also serve as the baseline exam;
15. Sputum will be induced using hypertonic saline for the assessment of the CFU for *PsA*. Patients with known intolerance to hypertonic saline will not undergo the procedure, as judged by their treating physician. A precise set of instructions will be provided and applied across sites to minimize sampling variations and ensure sputum sample quality;
16. Screening may be split into more than one visit and all results must be available prior to randomization so that the study Investigator can determine eligibility and schedule the baseline visit.

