2.7.1 Inclusion Criteria

Patients may be enrolled in and randomized to the study only if they meet all of the following criteria at screening:

1. Signed Informed Consent;
2. Adult men and women (as per State or Province laws) and 18 years and older;
3. Diagnosis of cystic fibrosis (positive sweat chloride test) or confirmation (can be historical) of two genetic mutations (one mutation on each of the two alleles of the CFTR gene) causing CF;
4. Screening FEV₁ between 40% and 100% predicted value for age, gender and height, in patients capable of properly performing the test, and baseline FEV₁ within 15% of the screening value, indicative of stable pulmonary function at entry;
5. History of pulmonary exacerbation, defined as at least one (1) pulmonary exacerbation in the 12 months prior to Screening which resulted in a documented IV antibiotic treatment;
6. Clinically stable patients, i.e. patients that had no change in their standard antibiotic medication within 5 weeks prior to randomization, of which 2 weeks minimum are prior to Screening;
7. Patients are eligible independently of their history of pulmonary PsA infection and their PsA status at screening. Medical charts will be reviewed for the PsA history in the 12 months prior to screening;
8. If taking Kalydeco® (ivacaftor), Orkambi® (ivacaftor/lumacaftor), Symdeko® (ivacaftor/tezacaftor) or another commercially available CFTR modulator product, patients must be taking it for a minimum of 3 months prior to screening if naïve to CFTR modulators and 1 month if switched from another CFTR modulator product, and deemed to tolerate it;
9. All patients, whether prescribed pancreatic enzyme replacement therapy or not, are eligible. However, modifications of the dosing regimen during the study should be avoided;
10. No change in CF and allowed systemic chronic therapy for a minimum of 5 weeks prior to randomization, of which 2 weeks minimum are prior to screening. Changes in non-CF therapy

may be allowed during this period, on a case-by-case basis, after consultation with Laurent Pharmaceuticals;

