2.8.1.2 Secondary Endpoints

- The proportion of patients achieving normalization of AA, DHA and the AA/DHA ratio in plasma phospholipids, LAU-7b compared to placebo. In this study, the normalization means a value or ratio value reaching the mean observed in healthy controls ± 1 SD;
- The absolute and relative (%) change from pre-study in FEV₁ percent predicted on Days 21, 49, 77, 105 and 189 visits (3, 7, 11, and 15 weeks during treatment and approximately 4 weeks after treatment, respectively), as well as the relative (%) change in FEV₁ % predicted on Day 161 (24 weeks), LAU-7b compared to placebo;
- The effect on the time to first protocol-defined PEx, LAU-7b compared to placebo;
- The effect on the incidence of protocol-defined PEx, LAU-7b compared to placebo;
- The effect on the time to first antibiotic use (other than chronic inhaled antibiotics already started prior to trial or oral chronic azithromycin), LAU-7b compared to placebo;
- The effect on the number of antibiotic treatments (other than chronic inhaled antibiotics already started prior to trial or oral chronic azithromycin), LAU-7b compared to placebo;
- The effect on the number of days of antibiotic treatment (other than chronic inhaled antibiotics already started prior to trial or oral chronic azithromycin), LAU-7b compared to placebo;
- The change from pre-study in systemic markers of inflammation in whole blood (total white cell count and absolute neutrophil count), serum (hsCRP and serum amyloid A), and plasma (calprotectin, haptoglobin, IL-1ra, IL-6, IL-8 IL-10, G-CSF, ceruloplasmin and neutrophil elastase antiprotease complexes), LAU-7b compared to placebo;
- The changes from pre-study in body weight and BMI, LAU-7b compared to placebo;
- The overall change in the *PsA* density in the sputum, from baseline through 12 and 24 weeks of treatment, when measured by the Area Under the Curve (AUC) of the CFU, LAU-7b compared to placebo;
- The fenretinide steady-state pharmacokinetics, depicted by C_{min} plasma concentrations at the end of the first and sixth treatment cycle;

- To assess the impact on overall health, daily life, perceived well-being and symptoms measured with the CFQ-R (total and respiratory domain) from pre-study to 12 and 24 weeks, LAU-7b compared to placebo.

2.8.1.3 *Exploratory Endpoints*

- The change from pre-study in AA, DHA and EPA in phospholipids and metabolipidomic markers (eicosanoids and docosanoids), LAU-7b compared to placebo;

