3.3 Analysis Population

The Intent-to-treat (ITT) Population will include all patients randomized to a treatment group who complete the baseline evaluations, regardless of having received any study treatment or not. The ITT population will be used for the primary analyses of all study endpoints, taking into consideration the specific populations described below. The patients will be kept in their randomized treatment arm for the analyses.

The Per Protocol (PP) Population will include all patients randomized to a treatment group to whom at least 5 cycles of study treatment are administered in accordance with the protocol, defined as at least 80% compliance. The PP population will serve as the basis for secondary analyses of

all study endpoints, taking into consideration the specific populations described below. The patients will be kept in the treatment arm that they actually received for the analyses.

The FEV₁ Population is a subset of the PP population and will include all patients who have validated FEV₁ values (values judged to be obtained from adequate expiratory curves by central review) for at least 4 time points of the study comprising at the minimum the baseline and Day 161 assessments. This population will be used for the secondary analyses of all FEV₁-related endpoints. The patients will be kept in the treatment arm that they actually received for the analyses.

The Protocol-Defined PEx Subset Population will include all patients who experience a protocol - defined PEx episode (\geq 4/12 Fuch symptoms and use of IV antibiotic) during the study after completing at least one cycle of study drug treatment. The patients will be kept in the treatment arm that they actually received for the analyses.

The Overall PEx Subset Population will include all patients who experience an oral or IV antibiotic treated PEx episode during the study after completing at least one cycle of study drug treatment. The patients will be kept in the treatment arm that they actually received for the analyses.

The Safety Population will include all patients randomized to a treatment group who received at least one dose of study drug treatment. This population will serve as the basis for analyses of all safety endpoints. The patients will be kept in the treatment arm that they actually received for the analyses.

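### The sputum PsA density comparison has no culture-positive set, no rule for no-growth samples and no baseline term, so it can lose either AUC power or the clearance signal

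*SAP*

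**What the plan says.** Enrolment ignores PsA. SAP 2.7.1, item 7: "Patients are eligible independently of their history of pulmonary PsA infection and their PsA status at screening". Protocol 8.1 has the same criterion.

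PsA density is a secondary endpoint in both documents, but the wording differs. SAP 2.8.1.2 has the change "when measured by the Area Under the Curve (AUC) of the CFU, LAU-7b compared to placebo"; Protocol 7.1.3 has it "when measured by the difference in the Area Under the Curve (AUC) of the CFU, LAU-7b compared to placebo". The analysis sits under the exploratory heading (Protocol 12.4.3, SAP 3.16).

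On population, SAP 3.16 says: "The analyses of the exploratory endpoints will be performed on both ITT and PP populations unless stated otherwise". Nothing is stated otherwise for PsA. ITT carries no culture condition: it is "all patients randomized to a treatment group who complete the baseline evaluations, regardless of having received any study treatment or not". SAP 3.3 defines special sets for FEV1, exacerbations, pharmacokinetics and healthy controls, but none for PsA.

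On method, SAP 3.16 says: "The mean changes and the AUC data will be compared between fenretinide and placebo using parametric statistics assuming the data meet standard pre-requisites". Those prerequisites are a normal or log-normal distribution and equal variances. "Area under the curve from baseline to Week 24, will be calculated with a linear trapezoidal method". Sputum is taken at screening, Day 77 and Day 161 (Protocol 10.5). Some patients will have no sample: "Patients with known intolerance to hypertonic saline will not undergo the procedure, as judged by their treating physician" (Protocol 9.2.1).

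Neither Protocol 10.5 and 12.4.3 nor SAP 3.16 states a detection limit, a value for no growth, whether the AUC is on raw or log CFU, or a baseline adjustment. The PsA text names no alternative test. By contrast, the exacerbation item in SAP 3.16 allows non-parametric statistics, SAP 3.17 allows alternative methods, and SAP 3.15 adds baseline covariates for weight, BMI and CFQ-R.

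**The concern.** The objective is whether LAU-7b affects lung colonisation with PsA (SAP 2.3.2, item 4). A patient with no PsA at entry cannot show a fall in density. A patient who clears PsA has the best possible result, and that result is a zero count, which has no logarithm. The plan puts both kinds of zero into a normal or log-normal comparison without saying how to score them.

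If zeros are kept at a low log value, the gap between infected and uninfected patients enters the variance of an unadjusted AUC and can swamp the treatment effect. If they become missing, successes are removed by a post-randomisation event that treatment may influence. The choice between these would be left to the analysis stage.

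**Working it through.** **Plan's own figure.** There is no sample size or power for PsA. The only one is for FEV1: 60 completers per group (SAP 2.6). With SD 8 and difference 4, n = 2(1.96 + 0.84)² × 8²/4² ≈ 63 per group (64 by exact t-test), so 60 is not quite reproduced; 60 gives 78.2% power (77.5% exact). The dropout step does reproduce: 120/0.90 = 134 after rounding up, then 136 as a multiple of 8. This matters here only as a source for n.

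**Check 1: closed form, no clearance.**

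*From the documents:* 60 completers per arm, two-sided 5%, three time points, linear trapezoid (time-normalised weights about 0.25, 0.50, 0.25).

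*Assumed:* share infected p; infected patients' log10 CFU mean 7, SD 1.5, correlation 0.6; effect 1.0 log10 at both later visits; no growth scored 0.

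AUC in infected patients:
- variance = 1.5² × [0.375 + 2 × 0.6 × 0.3125] = 2.25 × 0.75 = 1.69, SD 1.30
- effect = (0.50 + 0.25) × 1.0 = 0.75.

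At p = 0.7, infected only (42 per arm): SE = 1.30 × √(2/42) = 0.283; z = 2.65; power = Φ(2.65 − 1.96) = 75%.

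At p = 0.7, all 60 per arm:
- effect = 0.7 × 0.75 = 0.525
- variance = p × 1.69 + p(1 − p) × gap². Placebo (gap 7): 1.18 + 0.21 × 49 = 11.47, SD 3.39. LAU-7b (gap 6.25): 1.18 + 0.21 × 39.06 = 9.38
- SE = √((11.47 + 9.38)/60) = 0.590; z = 0.89; power = Φ(0.89 − 1.96) = 14%.

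| p | Infected only | All, no growth = 0 | All, no growth = 2 |
|---|---|---|---|
| 0.5 | 61% | 9% | 13% |
| 0.6 | 69% | 11% | 17% |
| 0.7 | 75% | 14% | 23% |
| 0.8 | 81% | 20% | 32% |
| 0.9 | 85% | 35% | 51% |

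With mean 6, SD 2 and no growth = 2 the loss is smaller: 39% to 15% (p = 0.5), 51% to 26% (0.7), 56% to 34% (0.8).

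Other readings of the same endpoint at p = 0.7, infected only against all:
- log AUC minus baseline: 97% against 96%
- log AUC with baseline as covariate: 99% against 98%
- AUC on raw CFU: about 3-5% either way
- change to Week 24: 93% against 91%, with the estimate falling from 1.0 to 0.7. The largest loss for the change test is about 7 points, at p = 0.4.

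**Check 2: simulation with clearance.** Assumed: 68 per arm, infected mean 6.5, SD 1.5, correlation 0.6, effect −1 log10, clearance by Day 161 of 15% (LAU-7b) against 5% (placebo), no growth at 1.7.

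- Unadjusted log AUC, all ITT against screening-positive: about 14-31% against 66-87% for 40-70% infected (18% against 73% at 50%), and 71% against 95% at 90% infected.
- With screening log10 CFU as covariate, 50% infected: 97% against 98%.
- Change test, 50% infected: 79% against 84%.

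The mean changes can be checked by hand:
- placebo, infected: 0.05 × (1.7 − 6.5) = −0.24
- LAU-7b, infected: 0.85 × (−1) + 0.15 × (−4.8) = −1.57
- difference: −1.33 in infected patients; × 0.5 = −0.67 in all patients at 50% infected (simulated −0.66)
- zeros dropped: only non-clearers remain, so about −1.0
- drug acts only through clearance: (0.15 − 0.05) × (−4.8) = −0.48 in infected patients; with zeros dropped, 0.

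**The case against.** The strongest reply is that the large power loss belongs to one reading only: an unadjusted AUC level, on the log scale, with no growth held at a low value. SAP 3.16 does not fix that reading. Subtracting baseline or using it as a covariate removes almost all of the loss even with every patient kept, and on raw CFU power is negligible with or without uninfected patients. This stands. A reader might infer that the AUC comparison simply loses most of its power; the documents do not support that as a flat statement, and at 90% infected the loss is moderate.

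Two other stronger readings also fail. A reader might infer that the change test is badly underpowered; it is not, because its SD shrinks along with its mean. A reader might also add the harms together, but they are alternatives. If zeros are kept, clearance counts. If logged zeros drop out, the uninfected drop out too, and there is no swamping or dilution.

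Further points deserve weight. The all-patient mean change is a legitimate ITT average, not a biased one. The parametric test is conditional on its prerequisites, which a spike of zeros would fail; the gap is that nothing is named to replace it. This is one of many endpoints tested at nominal 5% for signal detection (SAP 3.2), and the trial was not sized for it. The mock tables in SAP section 7 were not in the text available for this check, and sputum procedures are in the Study Reference Manual, so a scoring rule there cannot be excluded.

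None of this supplies the missing set, scale, no-growth value or covariate. SAP 3.15 specifies a baseline term for other endpoints, so an unadjusted PsA comparison is a natural reading of 3.16.

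**Conclusion.** The point holds in a conditional form and should be corrected. The text establishes that uninfected patients are eligible, that nothing removes them from the density comparison, and that no rule in the available sections scores a no-growth culture, adjusts for baseline or names a fallback.

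The consequence depends on the unwritten choice. With a floor on the log scale, an unadjusted AUC can fall to about 14-31% power from 66-87% (40-70% infected), or to 71% from 95% (90% infected). The mean change is then multiplied by the infected share, at a cost in power of about 5 points or less in most settings. With undefined logs dropped, a clearance-only effect of −0.48 log10 is estimated as 0.

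Prevalence, density, SD, correlation, effect, clearance rates and floor are all assumed. The direction of each harm follows from the plan's structure; the sizes do not.

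**What to change.** In SAP 3.16, specify for PsA density:

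- **Set:** ITT patients culture-positive for PsA at screening, a pre-randomisation criterion, for both change and AUC.
- **Scale:** log10 CFU, with the AUC computed on that scale.
- **No growth:** a fixed value, such as half the laboratory's detection limit, so that clearance counts.
- **Model:** treatment with screening log10 CFU as covariate. This recovers most of the AUC power (about 97-98% at 50% infected under the assumed inputs). Restricting the set adds little further power; its purpose is an estimate in patients whose density can fall.
- **Fallback:** a named rank-based test if the prerequisites fail.
- **Screening-negative patients:** frequency of culture conversion by arm, so that new colonisation is still reported.

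Patients never sampled because of saline intolerance fall outside this set.

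The cost is SAP wording and a population flag from a culture already scheduled, with no new visits or samples. The downside is that the density result applies to patients infected at entry, with a smaller n. If the mock tables already contain a rule, 3.16 should state it.

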10.5 Pseudomonas aeruginosa (PsA) density in sputum

Sputum will be obtained by hypertonic saline induction at time points listed in the Schedule of Events, Page 10, specifically at screening, Days 77 and 161 (Visits #1, 5 and 7, respectively) In order to minimize inter-site variability in the quality of the sputum samples, a protocol for inducing and obtaining sputum samples will be used across sites. It can be found in the Study Reference Manual. Training on the procedures will be provided to the clinical site staff.

The initial processing of the samples will be carried out at the clinical sites; the sputum induction will result in the patient producing a series of sputum samples. Upon obtaining the samples, their quality will be confirmed on the spot by macroscopic examination and weighing. Tubes containing suitable samples will be shipped overnight within 24 hours, in refrigerated state to the specialist laboratory [REDACTED], Denver, CO [REDACTED], USA.

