12 STATISTICAL ANALYSIS

A statistical analysis plan (SAP) will provide details of the methods of analysis to address all study objectives. The SAP may be amended during the course of the study, but will be finalized before the cutoff date for any analysis.

Data summaries by treatment group will be presented. For continuous variables, data will be summarized with the number of patients, mean, standard deviation, median, and minimum and maximum values by treatment group. For categorical variables, data will be tabulated in frequency tables to display the number and proportion of patients for each category by treatment group. Baseline assessments for each outcome variable will be defined as the last measurement obtained before the first dose of study drug except the baseline FEV₁ which will be the average of the screening and baseline best values, to reduce variability. Statistical significance will be set at the 5% level.

Diligent efforts will be made to prevent missing data in the study. For example, patients who discontinue the study treatment early or initiate medication changes (including those prohibited by the protocol) should still be followed for all regularly scheduled visits for safety and relevant efficacy assessments, or for a minimum of a 1-month follow-up. A clear distinction should be made between treatment discontinuation and study withdrawal. Efficacy assessments occurring after treatment discontinuation should not be included in the per-protocol analysis.

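### The AUC of sputum PsA counts is compared with no baseline adjustment and on an unfixed scale, so the comparison could miss a substantial effect

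*SAP*

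**What the plan says.** SAP 2.8.1.2 (like Protocol 7.1.3) lists PsA density among the secondary endpoints, "when measured by the Area Under the Curve (AUC) of the CFU, LAU-7b compared to placebo". The analysis itself sits under exploratory endpoints, in SAP 3.16 and Protocol 12.4.3.

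SAP 3.16 names three variables: "The overall change in the PsA density in the sputum, from Baseline to Week 12 and Week 24, and the AUC of the CFU". The AUC rule is: "Area under the curve from baseline to Week 24, will be calculated with a linear trapezoidal method". On the comparison it says: "The mean changes and the AUC data will be compared between fenretinide and placebo using parametric statistics assuming the data meet standard pre-requisites", the prerequisites being "normal or log-normal distribution and homogeneity of variance".

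Protocol 10.5 schedules sputum "specifically at screening, Days 77 and 161". Protocol 12 gives the general rule: "Baseline assessments for each outcome variable will be defined as the last measurement obtained before the first dose of study drug". No sputum is taken on Day 1, so baseline for this endpoint, and the first point of the AUC, is the screening sample.

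The PsA text names no covariate, baseline subtraction, analysis scale or rule for undetectable counts. Elsewhere the SAP does name a baseline covariate: for weight, BMI and CFQ-R in 3.15, and for AA, DHA and their ratio in 3.17.

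**The concern.** Bacterial counts vary between patients by orders of magnitude, and a patient's later count is likely to resemble the earlier one. An AUC that keeps the pre-treatment value and is not adjusted for it leaves this stable between-patient variation in the error term. It also dilutes any treatment effect, because the screening sample cannot carry one.

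The scale adds to this. The text describes an AUC of CFU, so the trapezoids sum untransformed counts and the largest cultures dominate. Taking logs of the finished AUC only partly undoes that. Patients are eligible whatever their PsA status (SAP 2.7.1), so zero counts are to be expected, and their logarithm is undefined without a rule.

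At stake is a listed secondary endpoint tied to a stated objective on lung colonization. The primary FEV₁ analysis is not affected.

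**Working it through.** **1. The plan's own figure.** There is none. The only power calculation in the documents is for FEV₁, and no SD, correlation, effect or usable number of patients is given for CFU. Every power below rests on assumed values.

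**2. Weight of the pre-treatment sample.** With sputum at day t₀, Day 77 and Day 161, the linear trapezoid gives the first sample the weight [(77 − t₀)/2] / (161 − t₀).
- Screening value placed at Day 1: 38/160 = 23.75%. Day 77 carries 80/160 = 50% and Day 161 carries 42/160 = 26.25%.
- Screening at Day −28: 52.5/189 = 27.8%.

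A constant effect is therefore diluted to 72–76% of its size.

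**3. Cost of the missing covariate on a log scale.** Assume SD 1, equal correlation ρ between visits, and the same effect δ at Days 77 and 161. Use weights w = (0.2375, 0.5, 0.2625), for which Σw² = 0.3753. Worked for ρ = 0.7:
- Unadjusted variance: ρ + (1 − ρ)Σw² = 0.7 + 0.3 × 0.3753 = 0.8126, SD 0.9014. Signal: 0.7625δ/0.9014 = 0.846δ.
- Covariance with baseline: 0.7 + 0.3 × 0.2375 = 0.7713. Adjusted variance: 0.8126 − 0.7713² = 0.2178, SD 0.4667. Signal: 0.7625δ/0.4667 = 1.634δ.
- Sample-size penalty for not adjusting: (1.634/0.846)² ≈ 3.73.
- If the adjusted test has 80% power (1.960 + 0.842 = 2.802), the unadjusted test has Φ(2.802/√3.73 − 1.960) = Φ(−0.51) ≈ 31%.

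| ρ | Unadjusted AUC of log10 CFU | Same, screening point removed, still unadjusted | AUC with baseline covariate | Penalty |
|---|---|---|---|---|
| 0.3 | 59% | 74% | 80% | 1.6 |
| 0.5 | 46% | 64% | 80% | 2.3 |
| 0.7 | 31% | 45% | 80% | 3.7 |
| 0.8 | 22% | 33% | 80% | 5.6 |

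The covariate restores the full 80% with the screening point kept. On the log scale that point is a multiple of the covariate, so once the covariate is in the model, keeping or dropping it does not change the test. Removing the point without adjusting recovers most of the loss only at the lowest correlation.

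**4. Adding the scale.** Simulation with log-normal counts, log10 SD 1.5, effect −0.7 log10 at both post-baseline visits, no zeros, two-sided 5%:

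| Test | ρ = 0.7, n = 40 / 60 per arm | ρ 0.3–0.8, n = 40–60 |
|---|---|---|
| t-test, AUC of raw CFU | 3.4% / 3.8% | about 3–7% (all raw-scale tests) |
| t-test, log of that AUC | 28% / 40% | about 27–52% |
| t-test, Week 24 change in log10 CFU | 76% / 91% | about 42–98% |
| ANCOVA, mean post-baseline log10 CFU | 92.5% / 98.9% | 79% to 99% or more |

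Repeat runs move these by a few points; one put the upper end for the log of the AUC at 49%. At ρ = 0.7, adding screening log10 CFU as a covariate to the log-of-AUC test alone lifts it to about 84–95%. The Week 24 change on raw CFU has about 3–4% power, so the change comparison helps only if it is made on the log scale.

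**The case against.** The strongest reply is that the AUC is not the only comparison. SAP 3.16 also compares mean changes to Weeks 12 and 24, which do use the screening value. On log10 CFU at a correlation of 0.7 the Week 24 change has 76–91% power, not far below ANCOVA. That stands, with two limits. The scale of the change is no more fixed than that of the AUC, and the AUC remains the measure named in the endpoint.

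Second, the parametric test is conditional on normal or log-normal data, so a t-test on raw counts this skewed would not meet the SAP's own condition. That also stands, and the raw-scale figure of 3–7% should not be read as the planned analysis. But the condition does not say what replaces the test, and taking logs of a raw-count AUC still leaves about 27–52%.

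Third, SAP 3.2 describes the non-primary analyses as mainly for signal detection, at a nominal 5% without multiplicity control. No success claim depends on this endpoint, which limits the severity.

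Fourth, the simulations contain no zero counts, although PsA-negative patients may enrol. The ANCOVA figures are therefore a best case.

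A reader might infer that the plan discards nearly all power, or that the endpoint would show no signal even with a real effect. The documents support neither. Near-total loss needs raw counts or a correlation near 0.9 (13% for the unadjusted log-scale AUC against 80% adjusted), the SAP leaves the scale open, and the change comparisons may detect the effect. Nor does the text forbid adjustment; it leaves it unspecified.

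**Conclusion.** The concern holds in limited form. The AUC comparison is specified without baseline adjustment or a fixed log scale, and it could miss a substantial effect on PsA. Under the assumed SD, effect and correlations, with 40–60 PsA-positive patients per arm, the log-transformed AUC has roughly a quarter to a half chance of detecting a 0.7 log10 reduction; adjusted analysis of the same samples has about 79% or more.

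The missing covariate and the raw scale account for most of this. The 24–28% weight on the screening sample is a lesser matter and does no harm once log10 baseline is a covariate in a log-scale analysis. The weights follow from the sampling days; all the powers depend on values the documents do not give. The point should be corrected, but it does not bear on the trial's primary conclusion.

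**What to change.** In SAP 3.16, specify log10 CFU as the analysis scale, with counts below detection set to a stated fixed value. Analyse Days 77 and 161 by ANCOVA or MMRM, with screening log10 CFU and the stratification factors as covariates. If an AUC is kept, compute it on log10 CFU with screening log10 CFU as a covariate. Apply the same scale and covariate to the Week 12 and Week 24 comparisons.

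The cost is SAP wording. The three sputum samples are already scheduled, so no visit, sample or patient is added. The text should be settled before unblinding, so that scale and covariates are not chosen with the results in view.
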